In order to accomplish treat-to-target recommendations for the management of SpA (Smolen et al 2014), a proportion of non-responder patients (i.e. patients not responding to 8 weeks of treatment with secukinumab 150 mg) will be assigned to an escalated dose of secukinumab (i.e. 300 mg) for 16 weeks (i.e. from Week 8 to Week 24) with the aim of exploring potential additional benefits in treatment adjustment and optimization. In addition, a proportion of patients from the placebo group will be assigned secukinumab 300 mg from Week 8 to Week 24 so as to explore the potential benefits of a higher dose of secukinumab (Section 3.3).

The regular assessments of disease activity ensure that safety will be monitored closely and both the patient and the investigator will have the opportunity to assess if the patient's continued participation in the study is to his/her benefit. If the patient's participation is

deemed not to be of benefit to him/her, the patient can exit the study at any time (see Section 5.6.2).

This study has been discussed by a Patient Associations' Steering Committee to guarantee that the study endpoints and the study conduct are fully aligned with patients' expectations and unmet clinical needs from a patient's perspective. The stratification criterion was chosen because previous TNF $\alpha$  exposure can have an influence on secukinumab response ([Baeten et al 2015](#)), and therefore allows for a balanced distribution between the verum and the placebo group.

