## 5.3 Treatment assignment and randomization

At Baseline, all eligible patients will be randomized to one of the treatment groups (Group A and Group B) via an Interactive Response Technology (IRT) system or similar system. The investigator or his/her delegate will contact the IRT after confirming that the patient fulfills all the inclusion/exclusion criteria. The IRT will assign a randomization number to the patient, which will be used to link the patient to a treatment group and will specify a unique medication number for the first package of study drug to be dispensed to the patient. The randomization number will not be communicated to the caller.

Randomization at Baseline will be stratified based on prior TNF $\alpha$  inhibitor exposure (i.e. according to whether patients are TNF $\alpha$  inhibitor naïve or TNF $\alpha$ -IR). It is assumed that approximately one third of the randomized patients will be TNF $\alpha$ -IR.

At Week 8, patients randomized to Group A (secukinumab 150 mg) at Baseline will be assessed for the achievement of spinal pain NRS score and will be classified as responders (spinal pain NRS score  $< 4$ ) or non-responders (spinal pain NRS score  $\geq 4$ ) and re-randomized or re-assigned via IRT to one of the treatment arms (Arm A1, Arm A2, Arm A3) as outlined in Section 5.2. At Week 8, patients randomized to Group B (placebo) at Baseline will be re-randomized via IRT to one of the 2 treatment arms (Arm B1 or Arm B2) as outlined in Section 5.2.

The IRT will be used to link the patient to a treatment group/arm and will specify unique medication numbers for the study drug to be dispensed to the patient. The randomization

numbers will not be communicated to the caller and will be generated using the following procedure to ensure that treatment assignment is unbiased and concealed from patients and investigator staff. A patient randomization list will be generated in collaboration with the IRT provider using a validated system that automates the random assignment of patient numbers to randomization numbers. These randomization numbers are linked to the different treatment groups/arms, which are in turn linked to medication numbers. A separate medication list will be produced in collaboration with Novartis Drug Supply Management using a validated system that automates the random assignment of medication numbers to packs containing the investigational drugs.

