Proportion of patients achieving a satisfactory Patient Acceptable Symptom State (PASS) at Week 1, 2, 3, 4 and 8 with secukinumab 150 mg compared to placebo.	Proportion of patients achieving a satisfactory PASS at Week 1, 2, 3, 4 and 8 in Group A compared to Group B.

Proportion of patients in each of treatment arm achieving a satisfactory PASS at Week 12, Week 20 and Week 24.	Proportion of patients achieving a satisfactory PASS at Week 12, Week 20 and Week 24 in Arm A1, Arm A2 vs Arm A3, and Arm B1 vs Arm B2.
Spinal pain NRS score according to previous exposure to tumor necrosis factor (TNF) inhibitors at Week 1, 2, 3, 4, 8, 12 and 24	Proportion of patients achieving a spinal pain score < 4 for TNF-naïve patients compared to TNF α -IR patients at Week 1, 2,3, 4, 8, 12 and Week 24
Proportion of patients who responded to secukinumab 150 mg at Week 8 (i.e. spinal pain score < 4 on a 0-10 NRS) maintaining a response at Week 24.	Proportion of patients with spinal pain score < 4 on a 0-10 NRS at Week 8 maintaining a spinal pain score < 4 at Week 24.
Proportion of patients achieving an improvement in ASAS health index with secukinumab 150 mg compared to placebo at Week 8.	Proportion of patients achieving an improvement in ASAS health index with secukinumab 150 mg compared to placebo at Week 8.
Proportion of patients achieving an improvement in ASAS health index in each treatment arm at Week 24.	Proportion of patients achieving an improvement in ASAS health index in each treatment arm at Week 24.
ASAS health index at Week 8 and Week 24.	Mean ASAS health index score in each treatment arm at Week 8 and Week 24
Change from baseline in total spinal pain NRS score at all time points.	Total spinal pain NRS score in each treatment arm at all time points.
Change from baseline in total BASDAI score at all time points.	Total BASDAI score in each treatment arm at all time points.
ASDAS-CRP at Week 8 and Week 24.	Mean ASDAS-CRP in each treatment arm at Week 8 and Week 24.
[REDACTED]	
[REDACTED]	
Safety and tolerability of secukinumab 150 mg and 300 mg over the study period.	Safety and tolerability, as measured by frequency and severity of adverse events and changes in laboratory values of interest for secukinumab 150 mg and placebo (Baseline to Week 8) and for secukinumab 150 mg and 300 mg (Week 8 to Week 24).

2 Statistical methods

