2.1 Data analysis general information

The data will be analyzed by Novartis and/or by the designated CRO (clinical research organization). It is planned that the data from all centers that participate in this protocol will be used for analysis. Analysis datasets and statistical outputs will be produced using the most recent SAS® Version 9.4 (SAS Institute Inc., Cary, NC, USA), and stored in Novartis global programming & statistical environment (GPS).

Summary statistics for continuous variables will include number of patients (n), mean, standard deviation, minimum, lower quartile, median, upper quartile, maximum. Summary statistics for discrete variables will be presented in the number and percent of patients in each category. Summary statistics will also be presented graphically wherever applicable.

The two-sided p-values and confidence interval (CI) will be presented.

Data analyses will be presented by treatment group for both period I and period II separately. Efficacy and safety data for the placebo-controlled period I will be presented by the following 2 treatment groups of A and B whereas for period II the data will be presented for 5 treatment groups A1, A2, A3, B1 and B2.

The analysis will be conducted on all patients' data at the time the trial ends (Week 24).

Comparative efficacy data

Comparative efficacy analyses (i.e. inferential efficacy comparisons with placebo) will focus on the Treatment Period 1, when active drug and the placebo are given in a manner suitable for making comparisons (i.e., first 8 weeks of treatment). Comparative efficacy will be performed based on the FAS-TP1 population using the randomized treatment for Treatment Period 1. After week 8 till week 24, the efficacy endpoints will be summarized descriptively or otherwise specified using inferential analysis, on the FAS population using the randomized/re-assigned treatment for Treatment Period 2.

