2.5.2 Statistical hypothesis, model, and method of analysis

The null hypothesis to be rejected is that the odds of response at Week 8 are equal in both treatment groups. The corresponding alternative hypothesis is that the odds of response at Week 8 are higher under secukinumab compared to placebo.

Let p_j denote the proportion of responders at Week 8 for treatment group j , $j=0, 1$, where

- 0 corresponds to placebo
- 1 corresponds to secukinumab

In statistical terms, the following hypothesis will be tested:

$H_0: (p_1 / (1 - p_1)) / (p_0 / (1 - p_0)) = 1$ versus $H_A: (p_1 / (1 - p_1)) / (p_0 / (1 - p_0)) \neq 1$

In other words,

H_A : The odds ratio of achieving a response at Week 8 for secukinumab vs. placebo is different from 1.

The primary analyses will be conducted via logistic regression model with treatment, country and the stratification factor of prior exposure to TNF inhibitors (naïve/ inadequate responders to TNF α inhibitors) as factor. The Odds ratio, 95% confidence interval (CI) and p-value will be presented comparing secukinumab 150 mg treatment group to placebo group at Week 8.

The null hypothesis of equal odds will be rejected if the 2-sided p-value from the logistic regression model for the factor “treatment” is < 0.05 ; however, superiority of secukinumab will be claimed only if the direction is correct, i.e. if the odds of response are larger under secukinumab.

Summary statistics will also be reported for each treatment group and by visit. Graphical representation will also be performed.

Grouping of countries: Due to the small number of subjects in some of the countries, the below mentioned countries will be grouped together to perform inferential analysis. The basis of grouping is a similar medical practice and geographical proximity in these countries:

- 1) Ireland & Great Britain
- 2) Italy, Spain & Croatia
- 3) Switzerland & Belgium
- 4) Finland & Sweden
- 5) Lithuania, Latvia & Estonia

If the grouping of countries does not allow proper analysis and if there are any challenges in model convergence, covariate “country” will be excluded from model.

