- Proportion of patients in each treatment group with response in spinal pain score < 4 at Week 24.
- Proportion of patients in each treatment group with response in BASDAI score < 4 at Week 24.
- Proportion of patients in each treatment group with response in ASDAS score < 2.1 at Week 8 and Week 24.
- Proportion of patients in each treatment group with response in ASDAS score < 1.3 at Week 8 and Week 24.
- Proportion of patients in Arm 1 with spinal pain score > 6 at Week 12 or Week 24.
- Proportion of patients achieving a spinal pain score < 4 for TNF-naïve patients compared to TNF α -inadequate responder (TNF α -IR) patients at Week 8 and Week 24.
- Proportion of patients with response in spinal pain score < 4 to secukinumab 150 mg at Week 8 maintaining a response at Week 24. Only descriptive statistics will be presented for this endpoint.

The statistical significance of the above endpoints between groups will be analyzed by 95% CI of proportion. P-value will be added if there are enough number of patients available. The following continuous exploratory endpoints will also be summarized descriptively with number of patients (n), minimum, mean, standard deviation, median and maximum.

- Change from baseline in spinal pain score according to previous exposure to tumor necrosis factor (TNF) blockers at Week 1, 2, 3, 4, 8, 12 and 24.
- Change from baseline in total spinal pain score at all time points by each treatment group for each treatment period.
- Change from baseline in total BASDAI score at all time points by each treatment group for each treatment period.
- Change from baseline in ASDAS-CRP at Week 8 and Week 24.

If for a significant number of patients, the assignment to responder and / or non-responder status is incorrect, then a risk analysis may be performed.

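### The exploratory TNF endpoint compares TNF-naïve with TNF-IR patients; no secukinumab–placebo effect within TNF stratum is planned, so the planned inference does not address effect modification

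*SAP*

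**What the plan says.** **The endpoint.** SAP 2.13 lists the "Proportion of patients achieving a spinal pain score < 4 for TNF-naïve patients compared to TNF"α-IR patients, at Weeks 8 and 24. SAP Table 1.2-1 pairs the same comparison with the objective "Spinal pain NRS score according to previous exposure to tumor necrosis factor (TNF) inhibitors at Week 1, 2, 3, 4, 8, 12 and 24". The Protocol summary also names response in naïve versus IR patients at Weeks 8 and 24 as an exploratory objective. Most neighbouring bullets in SAP 2.13 refer to each treatment group, and the others name an arm or a dose. This one names neither.

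**The inference.** For that list of categorical endpoints, SAP 2.13 states: "The statistical significance of the above endpoints between groups will be analyzed by 95% CI of proportion". A p-value follows if patient numbers allow. The groups are not defined for the TNF item. Change from baseline in pain by prior TNF exposure is listed separately, as a descriptive summary.

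**The general rules.** SAP 2.1 says "Data analyses will be presented by treatment group for both period I and period II separately", with Groups A and B shown in period I. It also says that "inferential efficacy comparisons with placebo) will focus on the Treatment Period 1".

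**The models.** The primary analysis is a "logistic regression model with treatment, country and the stratification factor of prior exposure to TNF inhibitors" (SAP 2.5.2). The repeated-measures model (SAP 2.13, 5.4.1) uses the same factors. TNF status enters as a main effect only.

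**The stratification.** Protocol 3.2 says that prior TNFα "exposure can have an influence on secukinumab response", and gives balance between active and placebo as what stratifying achieves.

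**The concern.** Whether prior TNF use changes what secukinumab does is a question about the secukinumab–placebo difference in each stratum. Stratified 3:1 randomisation gives a valid estimate of that difference up to Week 8. The endpoint instead compares two kinds of patient. TNF-IR patients may have a different prognosis whatever they receive, so a naïve–IR gap mixes prognosis with drug effect. It can appear when the drug works equally well in both strata, and it can be absent when the effect is lost in one of them.

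As written, the interval and possible p-value go with the naïve–IR gap, while the randomised contrast has no planned estimate. A lower response in TNF-IR patients could then be reported as a weaker drug effect on evidence that does not bear on it.

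**Working it through.** **Inputs from the documents.** Response 43.6% on secukinumab and 23.5% on placebo; 3:1 allocation; two-sided 5%; N = 332 evaluable, 352 recruited (Protocol 9.8, SAP 3). TNF-IR is "approximately one third of the randomized patients" (Protocol 5.3).

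**Plan's own figure.** With weighted mean p̄ = (0.235 + 3 × 0.436)/4 = 0.38575, the placebo group size is

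n₀ = [1.96√((4/3) × 0.38575 × 0.61425) + 1.2816√(0.235 × 0.765 + 0.436 × 0.564/3)]² / 0.201² = 76.4.

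Continuity correction: (76.4/4) × [1 + √(1 + 8/(76.4 × 3 × 0.201))]² = 82.9, so 83 placebo and 249 secukinumab, 332 in all. This matches and does not depend on the point raised here.

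**Stratum sizes at N = 352, one third TNF-IR.** Naïve 234.7 (176 secukinumab, 58.7 placebo); IR 117.3 (88 and 29.3).

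**What the naïve–IR gap measures** (stratum rates are assumptions):

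- *Same effect in both strata.* Naïve 48.6% vs 28.5%; IR 33.6% vs 13.5%. The effect is 20.1 points in each. Weighted 2:1, the arms average 43.6% and 23.5%, as planned.
  - Arms pooled 3:1: 43.6% naïve, 28.6% IR. The gap is 15.0 points, SE √(0.436 × 0.564/234.7 + 0.286 × 0.714/117.3) = 5.3 points, z = 2.8, p about 0.005.
  - Secukinumab arm alone: 48.6% − 33.6% = 15.0 points, SE √(0.486 × 0.514/176 + 0.336 × 0.664/88) = 6.3 points, z = 2.4, p about 0.02.
  - Odds ratios: naïve (0.486/0.514)/(0.285/0.715) = 2.4; IR (0.336/0.664)/(0.135/0.865) = 3.2. On the primary model's scale the effect is larger in IR, the reverse of what the raw gap suggests.
- *Effect lost in IR.* Naïve 43.6% vs 23.5%; IR 38.6% vs 38.6%. Pooled naïve response is 0.75 × 43.6 + 0.25 × 23.5 = 38.6%, the same as IR. The pooled gap is zero. Within the secukinumab arm it is 5 points, against a true difference in effect of 20.1 points.

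**What the randomised contrast can deliver by Week 8**, at 43.6% vs 23.5% in both strata:

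- *Within-stratum SE:* √(0.436 × 0.564/176 + 0.235 × 0.765/58.7) = 6.7 points naïve; √(0.436 × 0.564/88 + 0.235 × 0.765/29.3) = 9.4 points IR. Times 1.96, the 95% CI half-widths are 13.1 and 18.5 points.
- *Within-stratum power* (pooled-variance test, no continuity correction): Φ[(0.201√n₀ − 1.96 × 0.562)/0.512], giving 80% for n₀ = 58.7 and 49% for n₀ = 29.3.
- *Interaction, risk-difference scale:* SE √(6.7² + 9.4²) = about 11.6 points; CI half-width 22.7 points; detectable with 80% power (1.96 + 0.84) × 11.6 = 32.4 points.
- *Effect absent in IR* (23.5% in both arms): SE 11.2 points, z = 20.1/11.2 = 1.79, power Φ(1.79 − 1.96) = 43%. If the effect halves in IR (33.55% vs 23.5%), power is 14%.
- *Interaction, log-odds scale:* the planned log odds ratio is 0.92. SE = √Σ1/(np(1−p)) over the four cells = 0.595, so z = 1.55. Power for an interaction of that size is 34%.
- *TNF-IR share of 25% to 40%* (assumed range): IR-stratum power 38% to 57%; full-loss interaction power 38% to 46% on risk differences and 30% to 36% on log odds.

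**The case against.** **Display by arm.** A reader might infer that arms will be pooled and that the trial cannot show effect modification at all. The documents do not support that. The by-treatment-group rule in SAP 2.1 should yield Week 8 rates by arm within stratum, from which the differences could be read off. The pooled 15-point result with p about 0.005 is therefore an illustration, not established as planned output, and a p-value is conditional on numbers. This stands. It leaves the reader without a defined contrast or interval, and splitting by arm does not repair the naïve–IR comparison: in the first scenario the gap is still 15 points within secukinumab.

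**Purpose of stratifying.** A reader might also infer from Protocol 3.2 that the trial undertook to test effect modification. It did not. Balance is the stated purpose, stratified randomisation and the model term serve it, and no objective promises an interaction test.

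**Protocol objective.** The naïve–IR comparison is in the protocol, so deleting it from the SAP would drop a stated objective. This stands; the remedy should add to it.

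**Precision and stakes.** With about 29 placebo TNF-IR patients the interaction would probably be inconclusive, and the endpoint is exploratory, outside the confirmatory hierarchy. Both points stand. They argue for estimates with intervals and a stated warning.

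**Conclusion.** The concern holds in limited form. The named contrast is non-randomised and largely prognostic, and neither document plans a secukinumab–placebo estimate within TNF stratum or a treatment-by-TNF term. The planned inference therefore does not address whether prior TNF exposure modifies the drug effect, although the tabulated rates may allow an informal look.

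The 15-point illustration rests on assumed stratum rates. The precision figures rest on N = 352, one third TNF-IR and the plan's overall rates applying in both strata unless a loss of effect is specified. The primary test, the secondary test and the sample size are unaffected. This is a low-priority improvement to an exploratory analysis.

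**What to change.** 1. Keep the naïve versus IR summary, state that it is shown by arm within stratum, and label it descriptive, without a p-value.
2. For Weeks 1 to 8, add the Group A minus Group B risk difference and odds ratio with 95% CI in each TNF stratum.
3. Add a treatment-by-TNF term to the Week 8 logistic model as a separate descriptive analysis, leaving the primary model as it is. State beside it that power is about 34–43% even if the effect vanishes in TNF-IR and that the interaction CI half-width is about 23 points, so that a non-significant result is not read as no modification.
4. At Weeks 12 and 24, tabulate by arm within stratum only. No placebo remains, and for patients who started on secukinumab the dose depends on Week 8 response, so a naïve–IR contrast without arm could also mix in dose.

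The cost is one table, one extra model fit, edits to SAP 2.13 and Table 1.2-1, and an entry in SAP section 4, which now reports no changes. TNF stratum and treatment are already terms in the planned models. The protocol objective stays, and Protocol 9.6 leaves the detail of exploratory analyses to the SAP.

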## 1.2 Purpose

The purpose of the study is to evaluate the efficacy and safety of secukinumab 150 mg compared to placebo in the early management (Baseline to Week 8) of spinal pain, disease activity, fatigue and predictability of disease flares in patients with axSpA who have an inadequate response to prior NSAIDs. This study will also assess the efficacy and safety of secukinumab 300 mg compared to secukinumab 150 mg from Week 8 to Week 24 in order to assess the potential additional benefits of dose escalation in patients with axSpA.

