1.2 Study objectives and endpoints

Table 1.2-1 Objectives and related endpoints

Objective	Endpoint
Primary objective	
Superiority of secukinumab 150 mg compared to placebo in achieving a spinal pain score < 4 on a 0-10 NRS at Week 8.	Proportion of patients with a spinal pain NRS score < 4 at Week 8 in Group A compared to Group B.

Secondary objectives	
Superiority of secukinumab 150 mg compared to placebo in achieving a Bath Ankylosing Spondylitis Disease Activity Index (BASDAI) score < 4 at Week 8.	Proportion of patients with a BASDAI score < 4 at Week 8 in Group A compared to Group B.
Exploratory objectives	
Proportion of patients achieving a spinal pain score < 4 on a 0-10 NRS at Week 1, 2, 3 and 4 with secukinumab 150 mg compared to placebo.	Proportion of patients with a spinal pain NRS score < 4 in Group A compared to Group B at Week 1, 2, 3 and 4.
Proportion of patients in each treatment arm achieving a spinal pain score < 4 on a 0-10 NRS at Week 24.	Proportion of patients with a spinal pain NRS score < 4 in Arm A1, Arm A2 vs Arm A3, and Arm B1 vs Arm B2 at Week 24.
Proportion of patients in each treatment arm achieving BASDAI score < 4 at Week 24.	Proportion of patients achieving a BASDAI score < 4 in Arm A1, Arm A2 vs Arm A3, and Arm B1 vs Arm B2 at Week 24.
Proportion of patients in each of the treatment arms achieving Ankylosing Spondylitis Disease Activity Score (ASDAS) score < 2.1 at Week 8 and Week 24.	Proportion of patients with a ASDAS score < 2.1 in Group A compared to group B at Week 8 and in Arm A1, Arm A2 vs Arm A3, and Arm B1 vs Arm B2 at Week 8 and Week 24.
Proportion of patients in each treatment arm achieving ASDAS score < 1.3 at Week 8 and Week 24.	Proportion of patients with a ASDAS score < 1.3 in Group A compared to Group B at Week 8 and in Arm A1, Arm A2 vs Arm A3, and Arm B1 vs Arm B2 at Week 8 and Week 24.
Mean change from Baseline in functional assessment of chronic illness therapy-fatigue (FACIT-Fatigue [®]) score in patients on secukinumab 150 mg compared to placebo at Week 8.	FACIT-Fatigue [®] score in Group A compared to Group B at Week 8.
Mean change from Baseline in FACIT-Fatigue [®] score in each of treatment arm at Week 24.	FACIT-Fatigue [®] score in Arm A1, Arm A2 vs Arm A3, and Arm B1 vs Arm B2 at Week 24.
Proportion of patients in Arm A1 who have pain flares defined as NRS score > 6 at Week 12 or Week 24.	Proportion of patients who have pain flares, defined as NRS score > 6, in Arm A1 at Week 12 or Week 24.

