2.13 Other Exploratory analyses

All the exploratory efficacy evaluation will be performed on FAS-TP1 and FAS-TP2 population based on the corresponding treatment periods. Refer to [Table 1.2-1](#) of Section 1 for the list of exploratory endpoints.

The following exploratory efficacy variables will be analyzed on the FAS-TP1 and FAS-TP2 population at (Baseline to Week 8) and (Week 8 to Week 24) respectively for all applicable analysis visits unless otherwise specified.

- Spinal pain score: Average NRS spinal pain score will be calculated only if total and nocturnal pain score are non-missing.
- BASDAI score: It will be calculated based on the average of the non-missing answers available.
- ASDAS CRP
- Patient reported outcomes: FACIT-Fatigue[©], PASS, ASAS health index

- The average and raw (total and nocturnal) spinal pain NRS scores will be analyzed using a repeated measures analysis of variance (ANOVA) model with treatment, country and the stratification factor of prior exposure to TNF inhibitors (naïve/ inadequate responders to TNF α inhibitors) as factors and respective baseline NRS score as covariate. The least squares means of the two treatment groups, least squares mean difference and 95% confidence interval for the difference in the two treatment groups will be presented along with the p-value based on the fitted linear model.
- Formula for ASDAS-CRP calculation: ASDAS (CRP) = 0.121 x total back pain + 0,110 x patient global + 0.073 x peripheral pain/swelling + 0.058 x duration of morning stiffness + 0.579 x LN (CRP+1)
The parameters, which are taken from patient reported outcomes, are expected to have values 0-10. CRP needs to be in the unit mg/L.

All endpoints relating to exploratory objectives will be summarized descriptively. Summary statistics will include relative and absolute frequencies for the categorical variables and the number of patients (n), minimum, mean, median and maximum for continuous variables will be separately provided for both period I and period II. Time courses of response rates and mean NRS-scores will be displayed graphically.

The following categorical exploratory endpoints will also be summarized categorically as absolute and relative frequencies (proportions, %). Any improvement or reduction is referred to as 'response' for all the below mentioned endpoints.

- Proportion of patients in each treatment group with response in spinal pain score < 4 at Week 1, 2, 3 and 4.

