2.14 Interim analysis

No interim analysis is planned for this study.

3 Sample size calculation

To assess the assumed effect size at Week 8, a 43.6% response rate (spinal pain NRS < 4) is assumed for the secukinumab 150 mg group. This number is derived as an average of the response rates observed in the CAIN457F2320 and CAIN457F2310 studies ([Baeten et al 2015](#)). For the placebo group, a response rate at Week 8 of 23.5% (NRS < 4) was selected as assessed in the CAIN457F2320 study. This intermediate scenario takes into consideration a certain likelihood of a relatively high placebo response also in line with data from the TNF α reference studies and the CAIN457F2305 study in addition to the slightly milder course of the disease in the studied population ([Baeten et al 2015](#)).

Assuming conservatively a response rate of 23.5% in the placebo group and a response rate of 43.6% under secukinumab 150 mg, 332 patients in total (i.e. 249 patients in secukinumab 150 mg group and 83 patients in placebo group) would be needed under 3:1 (secukinumab: placebo) allocation to achieve 90% power on a (2-sided) 5% significance level. To compensate for drop-out patients or those with protocol deviations, a total of 352 patients (264 in secukinumab 150 mg group and 88 in the placebo group) should be recruited.

4 Change to protocol specified analyses

None.

5 Appendix

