5.4 Statistical models

5.4.1 Primary analysis

The null hypothesis to be rejected is that the odds of response at Week 8 are equal in both treatment groups. The corresponding alternative hypothesis is that the odds of response at Week 8 are higher under secukinumab compared to placebo.

The primary analyses will be conducted via logistic regression model with treatment, country and the stratification factor of prior exposure to TNF inhibitors (naïve/ inadequate responders to TNF α inhibitors) as factors. The Odds ratio, 95% confidence interval (CI) and p-value will be presented comparing secukinumab 150 mg treatment group to placebo group at Week 8.

SAS Code for logistic model

```
Proc logistic data=aaa;
Class TRT STRATA / param=glm;
Model AVAL = TRT COUNTRY STRATA;
Lsmeans TRT / diff cl exp;
Ods output diffs=lsm_diff;
Run;
```

In cases where separation is a concern for the primary endpoint at Week 8, e.g. 0% or 100% response in one treatment (sub)group, an exact logistic regression model will be applied to all visits. To ensure convergence, this model will not include any continuous covariates.

```
Proc logistic data=aaa exactonly;
Class TRT STRATA / param=glm;
Model AVAL = TRT COUNTRY STRATA;
Exact TRT / estimate=both;
Ods output exactoddsratio=exactoddsratio;
Run;
```

In addition to that the above analysis will also be performed a sensitivity analysis for raw spinal pain NRS score.

Mixed Model Repeated Measures (MMRM)

The following MMRM (or repeated measures ANOVA) model will be used for analysis of raw (total & nocturnal) and average spinal pain NRS score:

```
proc mixed data=.... order=internal;
where vis_1n in (2, 3, 4, 5, 6, 7);
class trt country strata;
model val_1n = trt bsval_1n country strata/ddfm=kr;
repeated vis_1n / subject=sid1a type=un;
lsmeans trt/ cl diff;
```

run;

If type=Unstructured (un) fails, we will use Compound Symmetry (cs)

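### SAP 2.13 and 5.4.1: the 300 mg v 150 mg contrasts in Treatment Period 2 are named for cut scores but not for full-scale NRS, BASDAI or ASDAS-CRP, and the scope of the NRS model is contradictory

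*SAP*

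**What the plan says.** Protocol 1.2 gives as a second purpose to "assess the efficacy and safety of secukinumab 300 mg compared to secukinumab 150 mg from Week 8 to Week 24". Group A non-responders and all Group B patients are re-randomised at Week 8, and Protocol 3.5 says this lets differences between the two regimens be explored.

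SAP Table 1.2-1 names the dose contrasts for the Week 24 spinal pain cut: "Proportion of patients with a spinal pain NRS score < 4 in Arm A1, Arm A2 vs Arm A3, and Arm B1 vs Arm B2". It does the same for BASDAI < 4 and for ASDAS < 2.1 and < 1.3. For full-scale spinal pain, BASDAI and ASDAS-CRP it lists only scores in each arm, with no contrast. FACIT-Fatigue is a full-scale score that does have the two contrasts named.

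SAP 2.13 then sets out three things:
- For the cut scores: "The statistical significance of the above endpoints between groups will be analyzed by 95% CI of proportion", with a p-value if there are enough patients (no threshold is given).
- For changes in spinal pain, BASDAI and ASDAS-CRP: "The following continuous exploratory endpoints will also be summarized descriptively with number of patients (n), minimum, mean, standard deviation, median and maximum".
- For the average, total and nocturnal NRS scores: a repeated-measures ANOVA reporting the "least squares mean difference and 95% confidence interval for the difference in the two treatment groups" and a p-value. The lead-in to this list covers both FAS-TP1 and FAS-TP2.

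The only code for that model, in SAP 5.4.1, begins "where vis_1n in (2, 3, 4, 5, 6, 7". Its fixed effects are treatment, baseline score, country and stratum.

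**The concern.** Patients in A2 and A3 enter Period 2 with NRS of 4 or more by construction. On the cut, a patient who falls from 8 to 4.5 counts the same as one who does not change. The pairs are small, so the choice of scale has a visible effect on precision.

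The plan is also open to two readings for NRS. One analyst could fit the repeated-measures model in Period 2 and another could leave it out, and both would be following the SAP. If it were fitted, the visits, the baseline covariate and the Week 24 contrast would have to be chosen after the fact. At stake is how precisely the trial can describe a dose difference that it re-randomises patients to study. No confirmatory result is affected.

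**Working it through.** **1. The plan's own figure.** SAP Section 3 sizes only the Week 8 comparison, at 43.6% v 23.5% and 3:1, "to achieve 90% power on a (2-sided) 5% significance level". Pooled rate = (0.235 + 3 × 0.436)/4 = 0.38575. The uncorrected placebo n = [1.960 × √(1.3333 × 0.2369) + 1.2816 × √(0.1798 + 0.2459/3)]² / 0.201² = 76.4, which rounds up to 77 (308 in total). With continuity correction, 76.4/4 × [1 + √(1 + 8/(76.4 × 3 × 0.201))]² = 82.9, giving 83 + 249 = 332. This matches the stated total. No figure is given for the dose comparison.

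**2. Arm sizes in Period 2.** Inputs are 264 and 88 recruited, and "a 43.6% response rate (spinal pain NRS < 4) is assumed for the secukinumab 150 mg group". Expected Group A non-responders = 264 × (1 − 0.436) = 148.9, about 74 per arm. Group B: 88/2 = 44 per arm. The 1:1 ratio is an assumption, because the documents do not state it. From the 332 evaluable patients the figures are about 70 and 41-42.

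**3. What the NRS code covers.** In Protocol Table 6-1, Visit 2 is Week 0 and Visit 7 is Week 8. If the code's visit variable follows that numbering, visits 2 to 7 end where Period 1 ends. With no visit or arm-by-visit term, lengthening the visit list would yield a difference averaged over visits, not one at Week 24. SAP 2.1.1 makes Week 8 the Period 2 baseline, but the model text says only that the respective baseline score is used.

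**4. Information kept by a cut.** For a normal score and a small shift, the fraction kept is φ(z)²/[p(1 − p)], where p is the response rate and z its normal quantile.

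| Week 24 response rate | Kept | Lost |
|---|---|---|
| 20% | 0.49 | 51% |
| 23.5% | 0.525 | 47.5% |
| 30% | 0.58 | 42% |
| 43.6% | 0.63 | 37% |
| 50% | 0.64 | 36% |

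A simulation of Week 8 non-responders on a rounded 0-10 scale (assumed SD 2.3, Week 8 to Week 24 correlation 0.5 or 0.7) gave losses of 34-42%.

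**5. Power, two-sided 5%.** The cut uses a two-proportion z-test with pooled null variance. The full score uses an unadjusted t-test with d = probit(p1) − probit(p0); for 25% v 40%, d = −0.253 + 0.674 = 0.42. The documents give no dose effect, so a range is shown.

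| Pair | 150 mg v 300 mg rate | Cut | Full score |
|---|---|---|---|
| A2 v A3 (74) | 20% v 35% | 53% | 79% |
| | 25% v 40% | 50% | 72% |
| | 30% v 45% | 47% | 67% |
| | 30% v 40% | 25% | 37% |
| B1 v B2 (44) | 25% v 40% | 32% | 50% |
| | 40% v 55% | 29% | 42% |
| | 43.6% v 53.6% | 15% | 21% |

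Simulated half-point scores for 25% v 40% agreed: 50% v 73% at 74 per arm and 34% v 49% at 44 per arm, with type I error near 5% for both tests.

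**6. Detectable at 80% power.** With 74 per arm, 0.46 SD on the full score or about 22-23 percentage points on the cut. With 44 per arm, 0.60 SD or about 29 points.

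**The case against.** A reader might infer that full-scale NRS is only described in Period 2. The documents do not support that. The SAP 2.13 lead-in includes FAS-TP2, the repeated-measures model sits under it, and the descriptive summaries are stated as an addition. A two-group difference could be read as A2 v A3 and B1 v B2 taken pairwise, and the code sits under the primary analysis heading, where it may serve only the Week 8 sensitivity analysis. This stands: for NRS the defect is unclear scope. It does not supply a Week 24 contrast, and it does not help BASDAI or ASDAS-CRP.

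A reader might also infer that the cut scores have a firm between-arm test. They have a confidence interval of a proportion, possibly per arm, and a conditional p-value, so even that inference is loosely specified.

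Nor is the information lost beyond recovery. The planned n, mean and SD by arm would let anyone compute an unadjusted difference and interval. That stands, although a difference derived afterwards is unadjusted and not prespecified.

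Finally, SAP 2.1 and Protocol 3.5 present Period 2 as largely descriptive, and NRS < 4 is the protocol's response definition. This is true and limits the weight of the point. But SAP 2.1 allows inference where specified, Protocol 9.6 allows inferential tests, and Table 1.2-1 already names the dose contrasts for the cuts.

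**Conclusion.** The point holds as a gap in specification with a measurable cost in precision. The dose contrasts are not named for full-scale NRS, BASDAI or ASDAS-CRP. The last two have no model in either period, and the NRS model as coded cannot give a Week 24 dose difference.

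Relying on the cut costs roughly 35-50% of the information. The loss is 37% at a 43.6% response rate and 51% at 20%, and over the scenarios tried the power difference runs from 6 to about 25 points. These sizes assume normal scores, no dropout, 1:1 re-randomisation and Week 24 rates that the documents do not give.

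A reader might infer that the full scale would make the dose comparison adequate. It would not: full-score power stays at 37-79% in A2/A3 and 21-50% in B1/B2. The small arms remain the main limit, and the comparison is exploratory either way. The change is worth making because it is cheap.

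**What to change.** Keep the Week 24 responder proportions. In SAP 2.13 add for FAS-TP2:

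- **Spinal pain NRS (average):** a repeated-measures model at Weeks 12, 20 and 24, fitted separately in A2/A3 and in B1/B2. Include arm, visit, arm-by-visit, TNF stratum, and the Baseline and Week 8 scores. Report the Week 24 least squares mean difference (300 mg minus 150 mg) with its 95% CI.
- **BASDAI:** the same model.
- **ASDAS-CRP:** an ANCOVA at Week 24 within each pair.

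Label all of these exploratory, and state in SAP 5.4.1 that the code for visits 2 to 7 applies to Period 1 only.

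The cost is SAP wording and a few extra outputs. Protocol Table 6-1 already schedules NRS and BASDAI at Weeks 12, 20 and 24 and the ASDAS components at Week 24, so there are no new patients or assessments, and no alpha is spent. The downside is additional exploratory results that rely on a missing-at-random assumption after dropout.
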